1.4 Summary and Hypothesis

Given the aforementioned data and relative lack of prospective studies regarding the use of MGX/IPL in patients with DED, we propose a prospective, randomized, case-controlled clinical pilot study to examine the efficacy of IPL for both subjective and objective measures. 20 patients with DED will be recruited, and will be randomly assigned to one of two groups: MGX alone, or MGX with IPL, and will undergo treatment every 4-6 weeks for 4 total treatment. Subjectively, participants will be scored using dry eye symptom questionnaires, including the OSDI, prior to treatment and post-treatment. Objective measures at baseline and at the end of the study will include tear cytokine levels, impression cytology for inflammatory markers, meibography, tear osmolarity, and ocular microbiome testing (see Chapter 2).

We hypothesize that use of MGX with IPL will lead to greater improvement in subjective dry eye symptoms, improved objective meibomian gland measures, and an upregulation in tear cytokines such as TGF-B1 and downregulation of inflammatory markers, such as IL-10, and improvement of ocular microbiome load, as compared to participants treated with MGX alone.

Given the lack of adverse effects reported in the literature, we do not anticipate study participants will experience adverse effects with proper performance of the IPL and testing procedures. For IPL subjects, masking using IPL-aid for both eyes will be used to protect the ocular structures. After Fitzpatrick skin type assessment, test application of IPL will be performed at the right preauricular skin and evaluated for erythema or skin change prior to

proceeding with the rest of the IPL application. We will record all events and include them in our analyses.

Chapter 2: Study Overview and Design

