2.4 Data Collection and Analysis

Appointment 1/Baseline. Data will be collected on the participants first visit ("baseline") and will include the following: OSDI, visual acuity, slit lamp imaging, lissamine green staining, fluorescein, tear film break up time (TBUT), Schirmers 5 minute with anesthesia osmolarity, meibography, Keratograph5 redness evaluation, Lipiview lipid tear film thickness, , tear cytokine evaluation and impression cytology (for flow cytometry of labeled cells for inflammatory markers), and tear sample for ocular microbiome testing.

number identifier, and their data will be entered into an Excel Document ("data file") and RedCap database which will be kept on a secure server at Mayo Clinic Arizona.

[figure not shown]
At appointment 1, participants will receive the initial treatment of either MGX or MGX+IPL. At appointment 1, participants will be given Tobramycin-Dexamethasone ophth soln to use BID topically OU for 2 days, and told to avoid UV exposure for 3 weeks.

Appointment 2. 4-6 weeks after appointment 1, at appointment 2, participants will be evaluated using OSDI, visual acuity, Icare tonometry, slit lamp imaging, lissamine green staining, fluorescein staining. This data will be entered into the data file. Participants will receive their second treatment of either MGX or MGX+IPL. At appointment 2, participants will be given Tobramycin-Dexamethasone ophth soln BID for 2 days, and told to avoid UV exposure for 3 weeks

Appointment 3. 4-6 weeks after appointment 2, at appointment 3, participants will be evaluated using OSDI, visual acuity, Icare tonometry, slit lamp imaging, lissamine green staining, fluorescein staining. This data will be entered into the data file. Participants will receive their second treatment of either MGX or MGX+IPL. At appointment 3, participants will be given Tobramycin-Dexamethasone ophth soln BID for 2 days, and told to avoid UV exposure for 3 weeks

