Appointment 4. 4-6 weeks after appointment 3, at appointment 4, participants will be evaluated with the following: OSDI, visual acuity, slit lamp imaging, lissamine green staining, fluorescein, tear film break up time (TBUT), Schirmers 5 minute with anesthesia osmolarity, meibography, Keratograph5 redness evaluation, Lipiview lipid tear film thickness, , tear cytokine evaluation and impression cytology (for flow cytometry of labeled cells for inflammatory markers), and tear sample for ocular microbiome testing. Participants will receive their final treatment of either MGX alone or MGX + IPL. At appointment 4, participants will be given Tobramycin-Dexamethasone ophth soln BID for 2 days, and told to avoid UV exposure for 3 weeks. (Data from Vegunta et al (2016) [19] proved that 3 treatments alone are sufficient to produce a symptomatic MGX/IPL response with improvement of dry eye symptoms and signs. We did not expect that subjects would be compliant to return for a 5th appointment if there was no treatment being performed at that visit.)

Data Analysis. After the completion of 4 treatments, and the collection of data as outlined above, data will be analyzed using statistical methods for changes to the aforementioned tests. The analysis will be conducted by a research trainee who will be blinded to the participant groups. That is, they will receive the identifiers "Group 1" vs "Group 2", without the identification of which group received MGX/IPL vs MGX alone.

ÌPL)

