3.2 Objective Parameters

Visual Acuity (VA). VA will be recorded in Snellen format for each eye as a safety measure. We hypothesize no changes to VA will be seen between groups. Cost for VA is estimated at \$20 for each test and will be bundled into OPH EST LIMITED EXAM CPT (see 3.3 below).

Applanation tonometry (TA). Recorded intraocular pressure (IOP) for each eye as measured by Goldmann applanation tonometry. IOP measurement and recording is a safety measure. We hypothesize no changes to IOP will be seen between groups. Cost for TA is estimated at \$20 for each test and will be bundled into OPH EST LIMITED EXAM CPT (see 3.3 below).

Conjunctival Injection Score (Redness). Analyzed using slit lamp images from Keratograph 5. Increased injection has been associated with increased DED symptoms. Score is graded as 0-3, with 0 being no conjunctival injection and 3 being marked injection. We hypothesize a decrease in conjunctival injection score with MGX/IPL versus MGX alone. Cost for conjunctival injection scoring is estimated at \$20 for each test and will be bundled into OPH EST LIMITED EXAM CPT (see 3.3 below).

Lissamine Green staining of the interpalpebral conjunctiva. Conjunctival staining is an effective tool to examine epithelial damage. It is easy to perform and has been proven with good reproducibility. We hypothesize an improvement in conjunctival staining with the use of MGX/IPL versus MGX alone. Two areas will be graded from 0-3 in severity. Cost for lissamine green staining is estimated at \$20 for each test and will be bundled into OPH EST LIMITED EXAM CPT (see 3.3 below).

Fluorescein Cornea Staining (FCS). Corneal staining is an effective tool to examine epithelial damage. It is easy to perform and has been proven with good reproducibility. We hypothesize an improvement in corneal staining with the use of MGX/IPL versus MGX alone. Five areas

each will be graded from 0-3 in severity. Cost for FCS is estimated at \$20 for each test and will be bundled into OPH EST LIMITED EXAM CPT (see 3.3 below).

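### The written visit lists name tonometry only at appointments 2 and 3, and MMP9 and QOL at no visit

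*Combined protocol and SAP*

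**What the plan says.** Section 3.2 treats IOP as safety data: "IOP measurement and recording is a safety measure. We hypothesize no changes to IOP will be seen between groups". It names the method: "Recorded intraocular pressure (IOP) for each eye as measured by Goldmann applanation tonometry".

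Section 2.4 gives a written list for each of four appointments:

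- Appointment 1 (baseline) begins "OSDI, visual acuity, slit lamp imaging, lissamine green staining, fluorescein, tear film break up time (TBUT), Schirmers 5 minute with anesthesia osmolarity, meibography" and goes on to redness, Lipiview, cytokines, impression cytology and a microbiome sample. It does not mention tonometry.
- Appointments 2 and 3 share a short list: "participants will be evaluated using OSDI, visual acuity, Icare tonometry, slit lamp imaging, lissamine green staining, fluorescein staining".
- Appointment 4 returns to the baseline list: "at appointment 4, participants will be evaluated with the following: OSDI, visual acuity, slit lamp imaging, lissamine green staining, fluorescein", and so on, again without tonometry.

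The analysis paragraph of 2.4 then says that "data will be analyzed using statistical methods for changes to the aforementioned tests".

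Two other measures are described but not placed at a visit. Section 3.2 has a paragraph on MMP9, which hypothesises a fall during the trial. QOL is in the endpoint list of 2.5, has an entry in 3.1 (with a price per test but no hypothesis), and its questionnaire is reproduced in 4.2.

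**The concern.** A safety measure needs a value before treatment and one at the end of observation. On the written lists IOP has neither. The planned analysis is of changes, and the only IOP change those lists allow is from appointment 2 to appointment 3, after treatment has begun.

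A comparison between arms does not replace the missing baseline. Sections 6.0 and 7.0 give both arms MGX and the same post-treatment drops, so an IOP shift common to both arms would cancel in the between-arm difference. Only change from baseline within each arm could show it.

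The two tonometry passages also name different devices. If both were used, a difference between readings could reflect the instrument. For MMP9, a hypothesis about change needs at least two time points, and the lists give none. For QOL, an endpoint has no stated collection time.

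**Working it through.** **Visit lists against the measures described**

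| Measure | Appt 1 | Appt 2 | Appt 3 | Appt 4 | Described in |
|---|---|---|---|---|---|
| Tonometry | no | Icare | Icare | no | 2.5; 3.2 (safety, Goldmann) |
| MMP9 | no | no | no | no | 3.2 only |
| QOL | no | no | no | no | 2.5, 3.1, 4.2 |
| Visual acuity, for comparison | yes | yes | yes | yes | 2.5; 3.2 (safety) |
| OSDI, for comparison | yes | yes | yes | yes | 2.5, 3.1 |

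Tonometry is named at 20 × 2 = 40 of 20 × 4 = 80 participant-visits. MMP9 and QOL are named at none.

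These are exceptions to the protocol's own pattern. Of the 14 objective measures in 3.2, 12 are named at both appointments 1 and 4; the other two are tonometry and MMP9. Visual acuity, the other measure that 3.2 labels as safety, is named at all four visits.

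**Timing.** At appointments 2 and 3 the assessments are listed before that visit's treatment. The two IOP readings therefore follow one and two treatments. Appointment 4, assessed after three treatments, has none.

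**Precision of the between-arm IOP comparison**

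The plan states no figure to reproduce. The only input from the documents is 10 per arm (2.3). The between-visit correlation r is assumed to be 0.5, 0.7 or 0.8, equal for all pairs of visits. The SD of a participant-level IOP value is assumed equal at all visits, and results are in units of that SD.

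- SE of a difference in means: √(2/10) = 0.447.
- One visit, unadjusted: t(0.975, 18) × 0.447 = 2.101 × 0.447 = 0.94.
- Mean of the two planned readings, unadjusted: 0.940 × √((1+r)/2).
- One visit, baseline-adjusted: t(0.975, 17) × 0.447 × √(1−r²) × √(1+1/16), with t = 2.110. The last factor is the expected penalty for chance baseline imbalance, 1/(N−4) at N = 20.
- Mean of two readings, baseline-adjusted: t(0.975, 17) × 0.447 × √((1+r)/2 − r²) × √(1+1/16).
- Within-arm change from baseline at one visit, n = 10: t(0.975, 9) × √(2(1−r)/10), with t = 2.262.

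| 95% half-width (SD units) | r = 0.5 | r = 0.7 | r = 0.8 |
|---|---|---|---|
| One visit, unadjusted | 0.94 | 0.94 | 0.94 |
| One visit, with baseline | 0.84 | 0.69 | 0.58 |
| Reduction | 10% | 26% | 38% |
| Mean of two readings, unadjusted | 0.81 | 0.87 | 0.89 |
| Mean of two readings, with baseline | 0.69 | 0.58 | 0.50 |
| Reduction | 15% | 33% | 44% |
| Within-arm change from baseline | 0.72 | 0.55 | 0.45 |

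The last row cannot be estimated at all from the written lists.

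**The case against.** The strongest reply is that this argues from silence in a section known to be incomplete. A figure in 2.4 is not reproduced in the text reviewed. The sentence that now starts "number identifier, and their data will be entered into an Excel Document" has lost its beginning, directly after the baseline list. The lists for appointments 1 and 4 each contain an empty slot, and the budget that 3.3 refers to is not included. Nor is the baseline list clearly exhaustive: it omits the Fitzpatrick typing that 6.0 and 7.0 require. The overview in 1.4 ("Objective measures at baseline and at the end of the study will include tear cytokine levels, impression cytology for inflammatory markers, meibography, tear osmolarity") is weaker evidence still, since it also leaves out tests that 2.4 does schedule.

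This stands as a limit on scope. A schedule in the missing material could name any of these items. It does not remove the point: one empty slot cannot hold three measures, and if the figure does schedule them, the written lists disagree with it and need correcting.

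Second, the IOP hypothesis in 3.2 is between groups, and two post-treatment readings in randomised arms can test it. That is right. What is lost is change from baseline, the last assessment and precision. The precision figures are in SD units for assumed correlations, and the documents give no IOP margin to judge them against.

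Third, the MMP9 and QOL gaps are largely clerical. MMP9 may be a leftover from a dropped test. QOL is priced and appended, and 1.4 plans symptom questionnaires before and after treatment, so collection was probably intended. But the instrument in 4.2 is a general quality-of-life survey, and no passage gives it a visit.

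**Conclusion.** The concern holds for the written lists. If they are followed, the IOP report is confined to a between-arm comparison after one and two treatments, unadjusted for baseline. It cannot say whether IOP rose or fell from baseline in either arm, or what it was at the last assessment. For a single visit the half-width of 0.94 SD is what a baseline reading would narrow by 10% to 38%, given assumed correlations of 0.5 to 0.8. The omission itself does not depend on those assumptions.

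The device conflict is in the visible text on both sides. The MMP9 hypothesis and the QOL endpoint have no scheduled data in the lists, but these two gaps matter less.

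The efficacy tests listed at appointments 1 and 4 are unaffected. This should be put right before the first treatment, because a baseline reading cannot be recovered afterwards.

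**What to change.** 1. In 2.4, add tonometry at appointment 1, before treatment, and at appointment 4. Report IOP as change from baseline in each arm and as a baseline-adjusted between-arm difference.
2. Reconcile the tonometry passages in 3.2 and 2.4 so that one device is used throughout.
3. Add MMP9 to appointments 1 and 4 and to 2.5, or delete its hypothesis from 3.2.
4. Add the QOL survey to appointments 1 and 4, or delete it from 2.5 and 3.1.
5. If the figure in 2.4 already schedules these items, bring the written lists into line with it.

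All additions fall at existing visits. At the protocol's $20 per test, each measure costs 20 participants × 2 visits × $20 = $800: $800 if only tonometry is added and the other two are deleted, or 3 × $800 = $2,400 if all three are added. The protocol describes these tests as bundled into the exam charge, so the extra money may be less. The other cost is slightly longer first and last visits.

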1.1 Introduction

Dry eye disease (DED) is a common condition that causes ocular discomfort and reduces visual acuity.[1] The two categories of dry eye disease are evaporative dry eye and aqueous deficient dry eye.[2] Both conditions can involve pathology of the meibomian glands, lacrimal glands, lids, tear film, and surface cells.[2, 3] Meibomian gland dysfunction (MGD) is the leading cause of evaporative dry eye[4] and contributes to aqueous deficient dry eye.[5]

Meibomian glands are modified sebaceous glands located along the upper and lower eyelid margins. Twenty to forty glands are located along each lid[6] and secrete meibum, the lipid component of tears.[7] MGD is defined by the International Workshop in Meibomian Gland Dysfunction[4] as the chronic, diffuse abnormality of the meibomian glands, commonly characterized by terminal duct obstruction and/or qualitative/quantitative changes in the glandular secretion. Patients may experience symptoms of eye irritation and clinically observable ocular surface disease and inflammation due to alteration of the tear film.

MGD is a commonly encountered disease by ophthalmologists. The impact of dry eye on quality-of-life is comparable to the effect of moderate to severe angina or dialysis treatment.[8, 9] The goal of MGD therapy is to provide long term improvement of symptoms for patients by improving the quality of meibum, increasing meibum flow, improving tear film stability, and decreasing inflammation. Commonly used therapies include preservative free drops, omega-3 fatty acid supplementation, topical cyclosporine, serum tears, topical azithromycin, oral doxycycline, moisture chambers, intraductal probing, lid margin exfoliation, automated thermal pulsation, warm compresses, and others. Despite the variety of treatment options available, patients often do not experience complete or long term relief of symptoms. Forced meibomian gland expression was first described in 1921 by [name] as an effective method of rehabilitating meibomian glands and improving dry eye symptoms in his patient.[10] The eyelid margins are forcefully compressed to express gland contents. Korb et al described an improvement in lipid layer thickness and symptoms in 10 patients with meibomian gland dysfunction treated with MGX.[11] Forced manual expression is painful for patients, and some of them are unable to tolerate the pain.

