Several prospective trials have been conducted on the efficacy of IPL (without MGX) for treating MGD. Craig et al. (2015) reported that IPL alone was effective in improving the lipid layer and patient symptoms.[16] In 2016, Jiang [17] enrolled 40 patients to receive IPL on day 1, day 15, day 45 and day 75. When compared to baseline measurements, significant improvements were found in both subjective symptomatic assessments and objective measurements of Meibomian gland secretion quality, TBUT, and conjunctival injection. While this study provided evidence of the benefit of IPL on MGD, its presents some limitations including a lack of control group and no analyses of inflammatory markers, or tear cytokines. In 2016, Gupta et al [18] conducted a cohort study of 100 patients with the diagnosis of MGD and DED who underwent an average of 4 IPL sessions. They reported a significant decrease in lid margin edema, lid margin vascularity, meibum viscosity and OSDI score, in addition to a significant increase in oil flow score and TBUT. Furthermore, in our previously published retrospective chart review of 35 patients with DED who were treated with serial IPL/MGX, we found a significant improvement in dry eye symptoms in 89% of patients and improvement in meibomian gland function in 77% of patients.[19]

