2.3 Participant Randomization

Once inclusion criteria have been met, patients will be randomized to one of two groups using a random number generator. 10 patients will be randomized to the control group, in which they will receive MGX every 4-6 weeks; and 10 patients will be randomized to the treatment group, in which they will receive MGX and IPL every 4-6 weeks. Biomarker and microbiome labs and data analyzer will be masked to treatment group.

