2.5 Design Summary

Power calculation for sample size for biostatistician

Range listed for endpoints

- OSDI (range 2-100)
- QOL
- VA - Slit lamp
- Slit lar
 TA
- Fluorescein (0-15)
- Lissamine Green (0-6)
- Lipiview (20-100)
- Tear Osmolarity (280-320)
- Meibography (0-100)
- Redness (Keratograph5)
- TBUT (0-10)
- Tear cytokines
- Impression Cytology for inflammatory markers
- Ocular microbiome testing

Chapter 3: Experimental Procedures and Cost

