Meibography Keratograph. Meibography is a tool to measure the amount of meibomium gland atrophy (MGA). MGA has been reported to be an important cause of dry eye.[27, 28] Images are objectively measured using ImageJ (NIH) based on a previously published report. [29] Results are reported from 0-100% atrophy of total surface area. We hypothesize a significant improvement in MGA with MGX/IPL versus MGX alone. Cost for meibography is estimated at \$20 for each test and will be bundled into OPH EST LIMITED EXAM CPT (see 3.3 below).

Lipiview. Lipiview measures lipid tear film thickness by interferometry on Lipiview instrument. Results are reported on a scale from 20-100. We hypothesize a decrease in the absolute thickness of tear film lipid layer with MGX/IPL versus MGX alone. Cost for lipiview is estimated at \$20 for each test and will be bundled into OPH EST LIMITED EXAM CPT (see 3.3 below).

Tear Cytokine. Tears will be collected at baseline and after the third treatment to be analyzed for the following markers: IL-1B, IL-6, IL-8, IL-10, IL-17, IFNg, TNFa, and TGFB1. Tear cytokine analysis of these markers has previously been shown as a marker of ocular surface inflammation, and is upregulated in DED.[30-33] We hypothesize an increase in TGFB1 and a decrease in the aforementioned inflammatory cytokines with MGX/IPL versus MGX alone. Samples will be collected at baseline and frozen at -80*C until analyzed using a pre-made custom plate (Millipore, USA). For 40 samples (20 patients x 2 samples each (1 pre and 1 post treatment), we will require 1 96-well plate at the cost of \$1500 + \$260 service fees. Additionally, to analyze TGFB1, we will require a separate plate at the cost of \$500 + \$300 for all samples. Therefore, the final cost for tear cytokine analysis will be \$2,560 for all samples for the entirety of the study.

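### The Lipiview hypothesis in Section 3.2 predicts a thinner lipid layer with IPL, which conflicts with the protocol's own rationale and is not explained

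*Combined protocol and SAP*

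**What the plan says.** The Lipiview entry in Section 3.2 describes lipid layer thickness measured by interferometry on a 20-100 scale, then gives the hypothesis: "We hypothesize a decrease in the absolute thickness of tear film lipid layer with MGX/IPL versus MGX alone". It does not say which end of the scale is favourable. Section 2.5 repeats the range and adds nothing on direction.

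The rationale is in Chapter 1. Section 1.1 says that the meibomian glands "secrete meibum, the lipid component of tears" and that the goals of therapy include "improving the quality of meibum, increasing meibum flow, improving tear film stability". It cites a small study (reference 11) that "described an improvement in lipid layer thickness and symptoms in 10 patients with meibomian gland dysfunction treated with MGX". Section 1.2 cites a prospective study reporting that "IPL alone was effective in improving the lipid layer and patient symptoms". Section 1.4 gives the overall hypothesis, that adding IPL to MGX will improve the objective gland measures.

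On analysis, Section 2.4 says only that "data will be analyzed using statistical methods for changes to the aforementioned tests". No test, sidedness or success rule is given for Lipiview.

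**The concern.** A directional hypothesis tells the analyst and the reader, before the data are seen, which result would support the treatment. If MGD means too little or poor-quality lipid reaching the tear film, and treatment is meant to restore it, a thicker lipid layer is the natural sign of benefit. The written hypothesis predicts the opposite and gives no reason.

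What is at stake is how the result is read. A report that holds the Lipiview result to the written sentence would present thinning as support for IPL and thickening as evidence against it. If the direction were reversed only after the results by arm had been seen, the change would look post hoc even if it were right.

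**Working it through.** The plan gives no effect size, standard deviation, alpha or power for Lipiview, so there is no stated figure to reproduce. The check is a comparison of every place that bears on direction.

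1. **Section 3.2, Lipiview entry.** Explicit direction: decrease with MGX/IPL relative to MGX. No reason and no favourable end of the scale.
2. **Section 2.5.** Range only. That list gives a direction for no endpoint.
3. **Section 1.1, meibum and goals of therapy.** Meibum is tear lipid, and treatment should raise its flow. More lipid delivered suggests a thicker layer. This is a physiological step that the protocol does not spell out.
4. **Section 1.1 with reference 11.** The text calls the effect of MGX on thickness an improvement. The cited source's title, as printed in the reference list, describes that effect as an increase. Read together, the protocol treats thicker as better. This is the strongest evidence.
5. **Section 1.2, IPL study.** The lipid layer improved, but no direction is given. The citation number attached to it (16) is printed in the reference list as a study of laser treatment for rosacea, so the direction cannot be traced. This item adds little.
6. **Section 1.4.** IPL is expected to improve objective gland measures. If thicker is better, predicting a thinner layer with added IPL amounts to predicting a worse result on this measure.
7. **Neighbouring entry.** In Section 3.2 the tear osmolarity hypothesis is also a decrease, but that entry labels the decrease as the improvement and states which values indicate severe disease. The Lipiview entry does neither.

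Items 3, 4 and 6 point to thickening as the benefit, item 5 is neutral, and nothing supports a decrease except the sentence in question.

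**Would the sentence change the test?** Only if the test were one-sided. As an illustration on assumed inputs, take a two-sample t-test with n = 10 per arm, 18 degrees of freedom, alpha 0.05, and a true thickening of d standard deviations. The noncentrality parameter is d × √(n/2) = d × √5, which is 1.118 at d = 0.5 and 2.683 at d = 1.2.

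| Assumed thickening | One-sided, decrease | One-sided, increase | Two-sided |
|---|---|---|---|
| 0.5 SD | 0.003 | 0.28 | 0.19 |
| 1.2 SD | 0.00001 | 0.83 | 0.72 |

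Entries are rejection probabilities. The two-sided column does not depend on the written direction. Only n comes from the protocol (Section 2.3).

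**The case against.** The strongest reply is that nothing in the documents contradicts the sentence outright. Sections 1.1 and 1.2 speak of improvement, not of a thicker layer. The only explicit mention of an increase in thickness is one reference title, for a study of 10 patients treated with MGX, which both arms receive. Meibum quality is listed as a goal separately from flow, and neither is mapped to the 20-100 scale. All of this stands: the conflict is inferred, and reference 11 shows which direction the protocol regards as better, not what IPL adds to MGX. It does not supply a reason for a decrease, and the protocol offers none.

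The reply also notes that the consequence is conditional and the endpoint carries little weight. That stands too. Section 1.4 does not name Lipiview among its objective measures, although it is collected at appointments 1 and 4 and listed in Section 2.5.

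Three stronger readings are tempting, and the documents do not support them:

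- **That the endpoint will be tested in the wrong direction with almost no power.** The one-sided column above might suggest this. No one-sided test is planned, and the alpha and effect sizes are assumptions, so those figures add nothing to the severity.
- **That Lipiview is the single hypothesis out of line with an otherwise consistent set.** Section 3.2 also predicts an increase in TGFB1 while listing it among markers described as raised in dry eye disease. That is a separate question, but it rules out presenting Lipiview as the sole exception.
- **That the sentence is certainly a slip of the pen.** A decrease may have been intended. The documents do not settle this, which is why the fix allows a justification instead of a correction.

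**Conclusion.** The point holds as a minor inconsistency. The only explicit statement of direction for Lipiview runs against the protocol's rationale and has no stated reason. The conclusion assumes that the protocol uses improvement in lipid layer thickness to mean a thicker layer, as the title of its own source indicates.

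The effect is confined to the interpretation of one unranked endpoint in a 20-patient pilot. It changes no sample size, allocation, visit or measurement, and no p-value if the test is two-sided.

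**What to change.** In the Lipiview entry of Section 3.2, either change the predicted decrease to an increase or add a sentence giving the reason for expecting a decrease. In the same entry, say which end of the 20-100 scale is favourable. No change to Section 2.5 is needed.

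Make the change before any Lipiview data are examined by arm. Unmasking of the group labels is not a safe cut-off, because the stated masking is limited: "Biomarker and microbiome labs and data analyzer will be masked to treatment group". Clinic staff who see Lipiview readings are not said to be masked.

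The cost is one word or one sentence of justification, plus one clause. Nothing changes in conduct, sample size or data collection.
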